16.3 Types of Data

Data for all subjects enrolled in this study will be obtained from thirteen sources: 1) the clinical microbiology laboratory; 2) initial subject screening phone call; 3) the Enrollment study visit and, for subjects enrolled prior to Day 5, phone call verification for no fever or worsening of symptoms; 4) Test of Cure Visit on Day 11 – 14; 5) Outcome Assessment Visit Day 24 - 30; 6) Follow-up Phone Call on Day 38 - 44; 7) the Pittsburgh Infectious Disease Research Laboratory (IDRL); 8) the subject medical record; 9) urinalysis; 10) urine culture; 11) three stool specimens ; and 12) medication diary. Study data will be collected on case report forms (CRF) designed for the study in an electronic data system. Data for this study will include safety, clinical laboratory, and outcome measures.

16.4 Timing/Reports

The CHOP Biostatistics and Data Management Core (BDMC) has developed a wide variety of status reports to monitor study progress. Study status of data management activities is provided on a frequent basis via a project status report. The report contains the number of CRF pages received, pages entered, pages reviewed, outstanding query

resolutions, and total number of subjects per site. These status reports will be made available to NIAID/DMID on a monthly basis. There are other possible status variables that NIAID/DMID might wish to monitor, and the BDMC will work with NIAID/DMID to define these reports.

The Westat Automated Report Portal (WARP) is a web-based service designed to provide users with an online reporting system. WARP delivers dynamic reports driven by project databases, as well as static documents such as PDF and MS-Word files. Dynamic reports can be programmed and run on-demand. Users simply enter pre-selected report parameters through the WARP user interface and receive dynamic output through their browser. Multiple output formats are available, such as HTML and PDF, and users can extract and download pre-programmed data via Excel files for additional processing.

Once half the subjects have completed the study, an interim analysis for the primary outcome measure will be performed.

At the conclusion of the study, a CD (or other media, if requested) will be sent to NIAID/DMID containing the following:

- Clinical datasets in SAS;
- SAS formats and catalogs; and
- Summary of transmitted datasets.

16.5 Study Records Retention

Study data, case report forms, and regulatory documents will be kept at the sites throughout the duration of the study. At the conclusion of the study, the records will be retained at archival storage places in accordance with the applicable FDA regulations (21 CFR 312.62) as paraphrased below:

- 1) For at least two years following the date on which the study product is approved by the FDA for marketing for the purposes specified in the clinical investigation; or
- 2) For at least two years following the date on which the entire clinical investigation (not just the investigator’s part in it) is terminated or discontinued. These documents will be retained for a longer period, however, if required by local regulations. No records will be destroyed without the written consent of the sponsor. It is the responsibility of the sponsor to inform the investigator when these documents no longer need to be retained.

16.6 Protocol Deviations

A protocol deviation is any noncompliance with the clinical trial protocol, Good Clinical Practice, or protocol specific Manual of Procedures. The noncompliance may be on the part of the subject, the investigator, or the study site staff. If study staff is unable to contact a subject requiring the day 5/6 contact before the subject starts the study product on day 6, it will be categorized as a protocol deviation.

All protocol deviations will be reported to DMID within five working days of identification of the protocol deviation, or within five working days of the scheduled protocol-required activity. All deviations from the Protocol must be addressed in the Subject Source Documentation. The documentation should include the reasons for the deviation and all attempts to prevent or correct them. Protocol deviation reports will be submitted as required by site IRBs.

17 PUBLICATION POLICY

Following completion of the study, the investigator will publish the results of this research in a scientific journal. The DMID will review the publication prior to submission to a scientific journal. The International Committee of Medical Journal Editors (ICMJE) member journals have adopted a trials-registration policy as a condition for publication. This protocol will be registered on ClinicalTrials.gov by the Principal Investigator, as sponsored by the National Library of Medicine, to meet publication requirements by the ICMJE. The ICMJE defines a clinical trial as any research project that prospectively assigns human participants to intervention or comparison groups to study the cause-and-effect relationship between a medical intervention and a health outcome.

Authorship of publications developed from this study will be determined by [name] in collaboration with [name]. Prior to submission for publication, articles will be submitted to DMID for review.

APPENDIX A: SCHEDULE OF EVENTS

APPENDIX B: SCOUT UTI TIMELINE DEFINITIONS

The SCOUT study is Phase II placebo-controlled randomized clinical trial. This section describes the design, objectives, outcomes, and treatments of this study as well as the study population and randomization. The definitions used for this study are also listed.

2.1 Project design

This is a multi-center, centrally randomized, double-blind, placebo-controlled non-inferiority clinical trial with children ages two months (at least 36 weeks gestational age birth for subjects < two years of age) to 10 years with a confirmed diagnosis of urinary tract infection (UTI). 724 children will be enrolled over a 4.5 year period and stratified based on presence of fever at the initial visit and by specific antibiotic therapy prescribed by the original treating clinical provider. At time of enrollment, children will be randomized to the standard course of antimicrobial therapy arm or the short course antimicrobial therapy arm. After the first 5 days of primary care physician initiated therapy, children who were randomized to the standard-of-care antimicrobial therapy arm continue on the same antibiotics for 5 more days and children who were randomized to the short-course antimicrobial therapy arm receive the placebo for 5 more days (for 10 days total).

2.2 Project objectives and outcomes

The primary, secondary, and sub-study objectives and outcomes of this study are as follows:

2.2.1 Primary objective

To determine if halting antimicrobial therapy in subjects who have exhibited clinical improvement 5 days after starting antibiotic therapy (short course therapy) have the same failure rate (symptomatic UTI) through test of cure (TOC) (visit Day 11-14) as subjects who continue to take antibiotics for an additional 5 days (standard course therapy).

2.2.2 Primary outcome

The primary efficacy outcome is symptomatic UTI as assessed at the TOC visit (Day 11-14).

2.2.3 Secondary objectives

- a.** To determine if short-course therapy compared to standard course therapy results in similar numbers of children experiencing a recurrent urinary tract infection (relapse and re-infection) at any time after TOC visit.
- b.** To determine if short-course therapy compared to standard course therapy results in similar numbers of children with asymptomatic bacteriuria at the TOC visit.
- c.** To determine if short-course therapy compared to standard course therapy results in similar numbers of children that become colonized with antimicrobial resistant *Escherichia coli* (*E. coli*) and *Klebsiella pneumoniae* (*K. pneumoniae*) in the gastrointestinal tract as assessed through Day 24-30.

- d. To determine if short-course therapy compared to standard course therapy results in similar numbers of children presenting with clinical symptoms that may be related to UTI prior to or at TOC visit.
- e. To determine if short-course therapy compared to standard course therapy results in similar numbers of children with positive urine culture prior to or at TOC.

2.2.4 Secondary outcomes

The secondary outcome measures are:

- a. Recurrent infection (includes a relapse UTI or a reinfection) at any time after the TOC visit (Day 11-14)
- b. Asymptomatic bacteriuria at the TOC visit
- c. Colonization with antimicrobial resistant E.coli and K. pneumoniae in the gastrointestinal tract as assessed through Day 24-30.
- d. Presentation of clinical symptoms that may be related to UTI prior to or at the TOC visit
- e. Positive urine culture prior to or at the TOC visit

2.2.5 Sub-study objectives

- To determine if E. coli and K. pneumoniae recovered from 2 or 3 stool cultures are more likely to be members of disease-associated subgroups within their respective species (E. coli phylogroups B2 and D, K. pneumoniae clusterKpI).
- To determine if treatment-susceptible strains recovered from cultures during treatment (culture #1 for 5-day arm; cultures #1 or #2, 10-day arm) are more likely to be members of disease-associated subgroups.
- To determine if treatment-resistant strains of either species are more likely than treatment susceptible strains to be recovered from cultures during treatment.

- To determine the overall prevalence of colonization with carbapenem-resistant Enterobacteriaceae (overall and for specific pathogens) in children after completion of the course of antibiotic therapy for UTI.
- To compare the overall biodiversity of the gut microbial community, as measured by culture-independent marker gene sequencing at each follow-up visit following short-course and standard-course antibiotic exposure.
- To compare the overall fraction of gut microbiome community represented by gammaproteobacteria measured by culture-independent marker gene sequencing at each follow-up visit following short-course and standard-course antibiotic exposure.
- To compare the average ecological similarity between microbial communities within and between treatment groups at each follow-up following short-course and standard-course antibiotic exposure.
- To describe the breadth of bacteria present in the stool of children receiving therapy for a urinary tract infection. These data will allow for comparison of aerobic bacteria composition in these children and present an opportunity to contrast them to similar data available from other pediatric patient populations.

2.2.6 Sub-study outcomes

The sub-study outcome measures are:

- Presence of E.coli and presence of K. pneumoniae
- Sub-types of E.coli (0=phylogroups A or B1, 1=phylogroups B2 or D), sub-types of K. pneumoniae
- Presence of treatment-susceptible E.coli, presence of treatment-susceptible K. pneumoniae
- Presence of treatment-resistant E.coli, presence of treatment-resistant K. pneumoniae

- Prevalence of colonization with carbapenem resistant Enterobacteriaceae in children after completion of the course of antibiotic therapy for UTI.
- Overall biodiversity of the gut microbial community, as measured by culture-independent marker gene sequencing.
- Overall fraction of gut microbiome community represented by gamma-proteobacteria measured by culture-independent marker gene sequencing.
- Average ecological similarity between microbial communities within and between treatment groups.
- Description of bacteria present on the aerobic stool cultures obtained at each of the three study timepoints.

2.3 Treatments

Short course therapy: prescribed antibiotic (Trimethoprim-Sulfamethoxazole (TMP-SMX), Amoxicillin-Clavulanate, Cefixime, Cefdinir or Cephalexin) for 5 days, followed by placebo for 5 days;

Standard therapy: prescribed antibiotic (TMP-SMX, Amoxicillin-Clavulanate, Cefixime, Cefdinir or Cephalexin) for 10 days.

2.4 Procedures

2.4.1 Study Population

Children: ages two months (at least 36 weeks gestational age at birth for subjects < two years of age) to 10 years with a confirmed diagnosis of a urinary tract infection (UTI) being treated by one of four antibiotics (TMP-SMX or Amoxicillin-Clavulanate or Cefixime or Cefdinir or Cephalexin). Only those subjects with documented clinical improvement (afebrile and asymptomatic) following four-five days of initial antibiotic therapy will be eligible.

2.4.2 Randomization and replacement

Children whose parents agree to participate in the study will be randomized to either (1) standard-of-care antimicrobial therapy (10 days of antibiotic therapy) or (2) short course antimicrobial therapy arm (five days of antibiotic therapy). We will stratify randomization within site based on (1) whether the UTI was originally associated with fever, and (2) the antibiotic prescribed at initiation of therapy. After treatment, the subjects will be followed for 38-44 days through follow-up phone calls and study visits. Subjects that withdraw or are withdrawn from the study prior to being evaluable for the primary outcome measure will be replaced. The study will continue until at least 652 subjects are evaluable for the primary outcome measure. At least 724 subjects will be enrolled in order to reach 652 evaluable subjects, but the total number that will be 'enrolled / consented' may exceed 724 if the study has not enrolled 652 evaluable for the primary endpoint.

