5 STUDY DESIGN

The SCOUT Study is a multi-center, centrally randomized, double-blind, placebo-controlled non-inferiority clinical trial. Children will be stratified based on the presence of fever at initial presentation of UTI symptoms and by specific antibiotic therapy prescribed by the original treating clinical provider. Children who have demonstrated clinical improvement five days after starting the originally prescribed antibiotic (afebrile and asymptomatic) will be randomized to standard arm or the short-course arm. Subjects enrolled prior to completion of Day 5 of their originally prescribed antibiotic treatment, will be instructed to complete Day 5 dosing prior to initiating SCOUT study product on Day 6. Subjects enrolled Day 6 should not have started the Day 6 of their originally prescribed antibiotic treatment. The SCOUT study product will consist of trimethoprim-sulfamethoxazole sulfamethoxazole (TMP-SMX), cefixime, cephalexin and the corresponding placebos. If a child initially prescribed cefdinir is enrolled, they will be randomized to either five additional days of cefixime or the cefixime placebo.

About 746 subjects will be enrolled in order to reach 672 evaluable subjects, but the total number that will be ‘enrolled / consented’ may exceed 746 if the study has not enrolled 672 evaluable for the primary endpoint.

Figure 1: Randomization

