6 STUDY ENROLLMENT AND WITHDRAWAL

The two participating clinical trial centers, CHOP and PITT will enroll subjects over an approximately four and a half year enrollment period until 672 subjects have been enrolled that are evaluable for the primary outcome measure.

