Safety Analysis: Safety in this study is related to efficacy. Safety will be evaluated by the collection and analysis of data on SAEs, clinical laboratory tests, pain assessments, and concomitant medications. The investigator is responsible for reporting all SAEs that are observed or reported up, regardless of their relationship to study product. Serious adverse events and abnormal laboratory (if available) results will be compared by treatment arm, with statistical tests for differences in proportion of subjects with serious adverse events between study arms.

Missing Data: Several procedures will be used to conduct data analysis when data for either outcomes or covariates are missing. The first step will be to assess the extent and pattern of missing data. If data are missing for only a few cases, then data analysis will be conducted only on study participants with complete data. However, when such a strategy would result in loss of data from a substantial proportion of participants or would lead to biased or inaccurate results, then some form of imputation will be performed. The form of imputation used will depend on the nature of the data that are missing.

Attrition and Loss to Follow-up: It is expected that loss to follow-up will be minimal in this study. Because the study is of short duration, we are hopeful that we will be able to follow virtually all subjects to study completion. However, some study participants may withdraw consent or may not return for the follow-up visits to determine the primary endpoint. Other participants may not have the endpoint determined due to problems with specimens or laboratory processing. We anticipate that these factors may reduce the sample size by as much as 10%. Thus the sample was increased by approximately 11% to offset this sample size reduction. Note that study participants who disrupt or discontinue study treatment will continue with follow-up and have the study endpoints assessed, and will be included in the ITT analysis.

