3.2 Sample size determination and power calculations

The primary aim of this study is to determine whether short-course antimicrobial therapy (five days) is non-inferior to standard-of care antimicrobial therapy (10

days) for the treatment of UTI in children with respect to reinfection of UTI through TOC visit Day 11-14. The treatment failure rate under the standard of care, R_0 , is expected to be 5%. This estimate is based on data from previously published studies [1, 2]. The power and sample size calculations are based on the assumption that recurrence under the short-course therapy, R_{SC} , will range from 5% to 9%.

In the non-inferiority test, on which power and sample size are based, the null hypothesis that short-course therapy is inferior to standard-of-care therapy is tested against the alternative that short-course therapy is non-inferior. That is, $H_0: R_{SC} > R_0 + \delta$ is tested against $H_a: R_{SC} \leq R_0 + \delta$, where δ is the “interval of equivalence,” the range in which the treatment failure rates of the two therapies would be considered clinically equivalent. We believe that an interval of equivalence of 5% would be clinically acceptable; a success rate of 95% for the standard-of-care therapy group when compared to 90% for the short-course therapy group. For all power and sample size calculations, the significance level (chance of incorrectly rejecting the null hypothesis) is $\alpha = 0.05$.

Table 1 gives the power for testing the non-inferiority hypothesis with a sample size of 300 evaluable subjects per arm and with equivalence intervals (i.e., δ) ranging from 2% to 5%. With 300 subjects per arm, there would be 87% power with $R_{SC} = 5\%$ and $\delta = 5\%$. The power decreases as either the equivalence interval decreases or as R_{SC} increases; in other words, as the recurrence rates of the two regimens become more similar, large sample sizes are required to discriminate between them.

Table 2 gives the sample sizes required to obtain 80% power with the same parameters for R_{SC} and δ . A sample size of 235 per arm is sufficient for 80% power with $R_{SC} = 5\%$ and $\delta = 5\%$, while larger sample sizes are required for larger values of R_{SC} or smaller values of δ . Finally, Table 3 gives the sample sizes required to obtain 90% power; a sample size of 326 subjects per arm would be required for 90% power with $R_{SC} = 5\%$ and $\delta = 5\%$.

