Based on these calculations, we propose a sample size of 326 per arm. However, this value must be adjusted upwards to offset loss to follow-up. It is expected that loss to follow-up will be minimal in this study. Because the study is of short duration, we are hopeful that we will be able to follow virtually all subjects to study completion. However, some study participants will not return for the follow-up visits to determine the primary endpoint. Furthermore, some percentage may need to disrupt or discontinue study treatment, or may not have the endpoint determined due to problems with specimens or laboratory processing. Altogether, these factors may reduce the sample size by as much as 10%. Thus we propose to increase the sample by approximately 11% to offset this sample size reduction, resulting in the final proposed sample size of 362 study participants per arm.

4. Statistical Analyses

The methods for the planned statistical interim analysis including the timing of the interim analysis, the scope of the interim analysis (a description of which endpoints will be analyzed), and the methods or statistical tests that will be used in the interim

analysis are described. The general description of the planned final analysis is provided.

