4.1 Interim Analysis

After half of the subjects (373 subjects) have enrolled, an interim analysis for the primary endpoint of treatment failure rate will be performed. This efficacy analysis will test the null hypothesis that the treatment failure rate under short-course therapy is less than or equal to that of standard-of-care therapy; the alternative hypothesis is that the failure rate under short-course therapy is greater than using standard-of-care therapy. This test will be one-sided test of hypothesis of equal treatment failure rates between the short-course therapy and standard-of-care therapy with $\alpha=0.05$. We will calculate the difference in treatment failure rates between short-course therapy and standard-of-care therapy, and a one-sided 95% lower confidence limit using normal approximation for large samples. If the lower confidence limit exceeds zero, we will conclude that short-course therapy has a significantly higher failure rate than standard-of-care therapy. Since the interim analysis is for superiority of standard-of-care therapy and the final efficacy analysis is for non-inferiority of short-course therapy, there is no impact of the interim analysis on the Type I error of the final efficacy analysis and thus no adjustments to the significance level are required.

In addition, conditional power estimates may be calculated. The conditional power analysis is a re-assessment of the power given the results of the study to date. If the recurrence rate for short course therapy is smaller than expected relative to standard therapy, then there would be high conditional power; if the recurrence rate for short course therapy is greater than expected relative to standard therapy, then there would be lower power than initially expected. The need for this analysis will be

decided in conjunction with the DSMB, along with other data to be presented to the DSMB.

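### The SAP's sample size (652 evaluable, 724 enrolled) disagrees with the protocol's 672 and 746 and with the SAP's own interim count of 373, and the interim trigger is worded two ways

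*SAP*

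**What the plan says.** **SAP, sample size.** Section 2.1 states that "724 children will be enrolled over a 4.5 year period". Section 2.4.2 adds the stopping condition: "The study will continue until at least 652 subjects are evaluable for the primary outcome measure". Section 3.2 gives the basis, namely that "a sample size of 326 subjects per arm would be required for 90% power" when both failure rates are 5% and the margin is 5 percentage points. It then allows about 11% for losses, "resulting in the final proposed sample size of 362 study participants per arm".

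**Protocol, sample size.** Section 5 says: "About 746 subjects will be enrolled in order to reach 672 evaluable subjects". Section 6 runs enrolment "until 672 subjects have been enrolled that are evaluable for the primary outcome measure". Section 12.4 describes the same allowance for losses: "Thus the sample was increased by approximately 11% to offset this sample size reduction".

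**Interim analysis.** SAP 4.1 places it as follows: "After half of the subjects (373 subjects) have enrolled". Protocol 12.3 opens with the same event, half enrolled, and links it to 336 evaluable children. Later in that section, where it leaves the timing to the SAP, it describes the timing as the point when half have completed the study. Protocol 16.4 repeats the completion wording.

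**The concern.** The documents carry two full sets of sample-size figures, and the SAP mixes them. Its design, replacement and power sections use the smaller set, while its interim section uses a count that fits only the larger one. A reader working from the SAP alone cannot reconcile half of the subjects with 373.

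These numbers govern when enrolment may end and when the only planned interim comparison of failure rates takes place. Between 652 and 672 evaluable children, the SAP's minimum has been met and the protocol's target has not. The interim look can be dated from enrolment or from completion, which are different days. Settling both in advance removes any later question of whether the stop or the look was influenced by the data. Protocol 16.1 also assigns the sample-size justification to the SAP, and the SAP currently justifies a size other than the one the protocol enrols.

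**Working it through.** **Inputs.** Standard-course failure rate 5%, short-course rate 5%, margin 0.05 and 90% power (SAP 3.2); one-sided alpha 0.05 (SAP 4.2.2); 1:1 allocation (Protocol Summary); losses up to 10%, with inflation of about 11% (SAP 3.2, Protocol 12.4).

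**1. Reproduce the SAP's figure.** Normal approximation, unpooled variance:

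n per arm = (1.645 + 1.2816)² × (2 × 0.05 × 0.95) / 0.05² = 325.4, rounded up to 326.

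This matches SAP 3.2. The 5% margin rows of SAP Tables 2 and 3 also reproduce exactly. One-sided 0.025 would give 400 per arm, so the SAP's figures rest on one-sided 0.05.

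**2. Apply the 11% inflation to each evaluable size.**

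| Source | Evaluable per arm | × 1.11 | Enrolled per arm | Evaluable total | Enrolled total | Half of enrolled |
|---|---|---|---|---|---|---|
| SAP 2.1, 2.4.2, 3.2 | 326 | 361.9 | 362 | 652 | 724 | 362 |
| Protocol 5, 6 | 336 | 373.0 | 373 | 672 | 746 | 373 |

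Each row is consistent in itself. The gap is 672 − 652 = 20 evaluable and 746 − 724 = 22 enrolled.

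**3. Place the interim count.** 373/746 = 50.0%, but 373/724 = 51.5%. With 10% lost, 373 × 0.9 = 335.7, which agrees with the 336 evaluable in Protocol 12.3; 362 × 0.9 = 325.8. The count in SAP 4.1 therefore belongs to the protocol's row.

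**4. Power at each size.** Power = Φ[(0.05 − (R_SC − 0.05)) / SE − 1.645], with SE = √{[0.05 × 0.95 + R_SC(1 − R_SC)] / n}.

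| Short-course rate | n = 326 | n = 336 |
|---|---|---|
| 5% | 90.0% | 90.8% |
| 6% | 72.4% | 73.6% |

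**5. Timing of the two triggers.** Assume even accrual of 746 over 4.5 years: 746 / (4.5 × 52.18 weeks) = 3.18 children per week. The Protocol Summary gives about five weeks per child.

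- From enrolment of the 373rd child to that child's completion: 5 weeks, 5 × 3.18 = 15.9, about 16 more children enrolled.
- If the half-enrolled look in any case waits for the test-of-cure visit (Day 11–14), the remaining wait to the final call (Day 38–44) is 27 to 30 days: 27/7 × 3.18 = 12.3 to 30/7 × 3.18 = 13.6, about 12 to 14 children.

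**The case against.** The strongest reply is that nothing is miscalculated and the documents can be obeyed together. The SAP's 652 and 724 are worded as minimums, and the SAP allows enrolment to exceed 724, so stopping at the protocol's 672 satisfies both. It remains true that 326 per arm gives 90% power, and 336 exceeds it. SAP 4.1 prints a definite count, 373, which agrees with the 336 evaluable in Protocol 12.3. No hypothesis, margin, alpha level, population or decision rule changes. The endpoint is read at test of cure, so the analysis could not take place on the day the 373rd child enrols, and five weeks is the upper end of the timing difference.

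Much of this stands. There is no power deficit, the effect is small, and the timing gap is better given as about four to five weeks. That the SAP was left behind when the protocol changed is only an inference, because no SAP date is visible; 373 being half of 746 suggests a partial update but does not prove it.

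The reply does not remove the mismatch. Within the SAP, 373 is not half of 724. The protocol text available here shows no calculation leading to 672, so the only derivation on file supports a different size. The protocol still gives two triggers, and one of them sits in the sentence that hands the timing to the SAP.

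**Conclusion.** The concern holds in all three parts: the SAP and protocol targets differ, the SAP's interim count is not half of its own total, and the trigger is worded two ways. It is a fault of consistency in figures the trial relies on, not an error in the 326.

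Its size is modest. The power difference is 0.8 points at equal 5% rates and 1.2 points at a 6% short-course rate, on the normal approximation at one-sided 0.05. The timing figures assume even accrual and are indicative only. The point should be corrected because the numbers end enrolment and date the interim look, but it does not by itself threaten the trial's conclusion.

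**What to change.** 1. **One sample size.** Bring SAP 2.1, 2.4.2 and 3.2 into line with the protocol: 672 evaluable (336 per arm), about 746 enrolled (373 per arm), and power of about 90.8% at 5% in both arms. Add a sentence giving the reason for 672, since 652 already reaches 90%. State one evaluable number that ends enrolment.
2. **Interim count.** Keep 373 enrolled, expected to yield about 336 evaluable, and give 746 as the total it is half of.
3. **One trigger.** Use the same event, half enrolled or half completed, in Protocol 12.3, Protocol 16.4 and SAP 4.1. If it is half enrolled, say that the analysis follows once those children's test-of-cure outcomes are available.

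If 652 and 724 are what is intended, correct the Protocol Summary and Protocol 5 and 6 instead, change the 336 in Protocol 12.3 to 326, and set the interim in SAP 4.1 at 362 enrolled.

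**Cost.** The first route is wording only, in the SAP and in the interim-timing sentences of Protocol 12.3 and 16.4, with no children beyond the protocol's target. The second route touches more protocol sections and lowers the enrolment target by 22.
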